5.4.1.3.6. Time to First Virologic Breakthrough

Time to first HBV virologic breakthrough will be defined as the number of days between the date of first study intervention intake and the date of the first occurrence of virologic breakthrough (i.e. the date of the first virologic breakthrough [the first of the two confirmation visits] - the date of first study intervention intake +1). The participants who withdrew early from the study before experiencing virologic breakthrough or who did not experience virologic breakthrough will be censored at the last available HBV DNA assessment at or before EOT.

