1.1. Objectives and Endpoints

Objectives	Endpoints
Primary	

 To evaluate the efficacy in terms of HBsAg levels of the study intervention (i.e. JNJ-3989 + JNJ-6379^d + NA and PegIFN-α2a). 	
 Proportion of participants with a reduction of at least 2 log₁₀ IU/mL in HBsAg levels from baseline to Week 24 (end of study intervention [EOSI]).
Secondary	

 To evaluate the safety and tolerability of the study intervention. 	
 Safety and tolerability including but not limited to the proportion of participants with (serious) adverse events (S)AEs and abnormalities in clinical laboratory tests (including hematology, blood biochemistry, blood coagulation, urinalysis, urine chemistry, and renal biomarkers), 12-lead electrocardiograms (ECGs), vital signs, and ophthalmic and physical examinations throughout the study.

 To evaluate the efficacy of the study intervention at the end of the 24-week treatment period. 	
 Proportion of participants meeting the protocol-defined NA treatment completion criteria at EOSI.

 To evaluate the efficacy of the study intervention as measured by blood markers (such as HBsAg, HBeAg^a, HBV DNA, and alanine aminotransferase [ALT]) during the study intervention and follow-up (FU) period. 	
 Proportion of participants with HBeAg^a, HBsAg, HBV DNA, and ALT levels below/above different cut-offs. Proportion of participants with HBsAg and/or HBeAg^a seroconversion.

Objectives	Endpoints
	
 Change from baseline over time in HBsAg, HBeAg^a, and/or HBV DNA. Time to achieve HBsAg and/or HBeAg^a seroclearance/seroconversion, and/or HBV DNA < lower limit of quantification (LLOQ).

 To evaluate the frequency of virologic breakthrough^b during the 24-week treatment period, as well as during the FU period for participants who continue treatment with NA. 	
 Proportion of participants with virologic breakthrough^b.

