1.2. Study Design

This is a Phase 2a, open-label, single-arm, multicenter study to assess efficacy, safety, tolerability and pharmacokinetics of treatment with JNJ-3989, JNJ-6379 (as applicable), NA, and PegIFN- α 2a in virologically suppressed patients with chronic hepatitis B virus infection. Prior to Protocol Amendment 3, the study intervention also included JNJ-6379. Note that as of Protocol Amendment 3, JNJ-6379 has been removed as study intervention and the study will continue with JNJ-3989, NA and PegIFN- α 2a only. Participants had to stop JNJ-6379 treatment immediately after the implementation of Urgent Safety Measure (USM) and approval of the protocol amendment 3.

Approximately 50 virologically suppressed CHB-infected participants, 18-65 years (inclusive) of age, will be enrolled in this study. Approximately 40% HBeAg-positive participants will be enrolled.

[figure not shown]
The study will be conducted in 4 periods:

- Screening period (4 weeks [if necessary, can be extended to a maximum of 8 weeks decided on a case-by-case basis and in agreement with the sponsor]).
- Treatment Period 1 (12 weeks) consisting of combination treatment with JNJ-3989 + NA.
- Treatment Period 2 (12 weeks) adding PegIFN- α 2a to the combination treatment regimen of Treatment Period 1.
- Follow-up (FU) Period (48 weeks).

The total duration of individual participation will be up to 76 weeks (including 4 weeks of screening).

A schematic of the trial prior to Protocol Amendment 3 is presented in [Figure 1](#).

Figure 1: Schematic Overview of the Study – Prior to Protocol Amendment 3

[figure not shown]

ALT: alanine aminotransferase; DNA: deoxyribonucleic acid; EOS: end of study; EOSI: end of study intervention; FU: follow-up; HBeAg: hepatitis B e antigen; HBsAg: hepatitis B surface antigen; HBV: hepatitis B virus; JNJ-3989: JNJ-73763989; JNJ-6379: JNJ-56136379; LLOQ: lower limit of quantification; n: number of participants; NA: nucleos(t)ide analog; PegIFN-α2a: pegylated interferon alpha-2a; ULN: upper limit of normal; Q4W: every 4 weeks; QD: once daily; QW: once weekly.

^a. If NA treatment completion criteria (HBsAg <10 IU/mL, and HBeAg-negative, and HBV DNA <LLOQ, and ALT <3x ULN) have been met at Week 24, NA will be stopped at the next scheduled visit (ie, FU Week 2), otherwise NA treatment will continue during the complete FU period.

A schematic of the trial as of Protocol Amendment 3 is presented in [Figure 2](#).

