5.4.1.1.15. Virologic Breakthrough

HBV virological breakthrough is defined as having a confirmed on-treatment HBV DNA increase by $>1 \log_{10}$ from nadir level (lowest level reached during treatment) in participants who didn't have on-treatment HBV DNA level below the lower limit of quantification (LLOQ) or a confirmed on-treatment HBV DNA level >200 IU/mL in participants who had on-treatment HBV DNA level below the lower limit of quantification (LLOQ). Confirmed HBV DNA increase/level means that the criterion should be fulfilled at 2 or more consecutive time points or at the last observed on-treatment time point. On-treatment will be defined as the time period in which the participant receives any of the study interventions (including NA).

In addition, participants who experience a virologic breakthrough followed by on-treatment biochemical flare will be evaluated.

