- 1 (Yes) = confirmed** ALT and/or AST $\geq 3x$ ULN and $\geq 3x$ nadir (i.e. lowest value observed up to the start of flare)
- 0 (No) = otherwise

4. Clinical flare is defined as follows:

A clinical flare occurs either when a virologic flare and biochemical flare overlap in time or when a biochemical flare starts within 4 weeks following the end of a virologic flare. The start date of a clinical flare is defined as the minimum start date of the virologic flare and the biochemical flare. The end date of a clinical flare is defined as the maximum end date of the virologic flare and biochemical flare, i.e., the later date of HBV DNA returns to ≤ 200 IU/mL and 50% reduction from the peak ALT and/or AST level.

- 1 (Yes) = confirmed** HBV DNA $>$ peak threshold and confirmed** ALT and/or AST $\geq 3x$ ULN and confirmed** $\geq 3x$ nadir (i.e. lowest value during study participation).
- 0 (No) = otherwise

** Confirmed means that the criterion should be fulfilled at 2 or more consecutive time points or at the last observed time point.

The virologic and clinical flares will be assessed only off-treatment, while biochemical flares will be identified on-treatment and off-treatment. On-treatment virologic flares are described as virologic breakthrough in Section 5.4.1.1.15. On-treatment will be defined as the time period in which the participant receives any of the study interventions. Off-treatment will be defined as the period after stopping all study interventions (including NA).

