5.4.1.3.7. Time to First Flare

Time to first biochemical flare (on- and off-treatment), clinical flare off-treatment, and virologic flare off-treatment will be evaluated.

Time to first on-treatment flare will be defined as the number of days between the date of first study intervention intake and the date of the first occurrence of on-treatment flare (i.e. the date of the first on-treatment flare [the first of the two confirmation visits] of each type- the date of first study intervention intake+1). The participants who withdrew early from the study before experiencing on-treatment flare or who did not experience on-treatment flare will be censored at the last available blood markers or liver enzymes assessment at or before EOT.

Time to the first off-treatment flare will be defined as the number of days between the date of last study intervention intake and the date of the first occurrence of off-treatment flare (i.e. the date of experiencing the first off-treatment flare [the first of the two confirmation visits] of each type- the date of last study intervention intake). The participants who withdrew early from the study before experiencing off-treatment flare or who did not experience off-treatment flare will be censored at the last available blood markers or liver enzymes assessment.

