5.5.1.5. Sustained HBsAg Response

The definitions of sustained HBsAg response are as follows:

- Definition #1:
 - For participants with Follow-up Week 48 data: participants who had a $>1 \log_{10}$ decline from baseline in HBsAg at Follow-up Week 48 and HBsAg $< 1,000$ IU/mL at Follow-up Week 48.
 - For participants without Follow-up Week 48 data: participants who had a $>2 \log_{10}$ decline from baseline in HBsAg at Follow-up Week 24 or a $>1.5 \log_{10}$ decline in HBsAg at Follow-up Week 36 (most recent value used) and had HBsAg $< 1,000$ IU/mL at the last available timepoint.
- Definition #2:
 - For participants with a $>1 \log_{10}$ decline from baseline in HBsAg at the last Follow-up visit: among the 3 most recent visits, the difference between \log_{10} HBsAg at 2 of the 3 last visits and 1 of the 3 last visits is $< 0.2 \log_{10}$ IU/mL and the difference between \log_{10} HBsAg at 3 of the 3 last visits and 1 of the 3 last visits is $< 0.2 \log_{10}$ IU/mL.
- Definition #3:
 - For participants with a $>1 \log_{10}$ decline from baseline in HBsAg at the last Follow-up visit: among the 3 most recent visits, the difference between \log_{10} HBsAg at 2 of the 3 last visits and 1 of the 3 last visits is $< 0.2 \log_{10}$ IU/mL and the difference between \log_{10} HBsAg at 3 of the 3 last visits and 1 of the 3 last visits is $< 0.2 \log_{10}$ IU/mL and had HBsAg $< 1,000$ IU/mL at the last available timepoint.
- Definition #4:

- Three categories regarding the difference between HBsAg level at the last Follow-up timepoint and Week 24 (EOT):
 - $>0.2 \log_{10}$ decrease: Decreasing level
 - $\leq 0.2 \log_{10}$ increase or $\leq 0.2 \log_{10}$ decrease: Stable level
 - $\leq 0.2 \log_{10}$ increase or $\geq 0.2 \log_{10}$ decrease: Stable or Decreasing level
 - $>0.2 \log_{10}$ increase: Increasing level

For all definitions of the sustained HBsAg response, only participants with at least 24 weeks of follow-up data after JNJ-3989 stop will be used for the analysis.

The count and proportion (%) of participants achieving sustained HBsAg response will be summarized.

Spaghetti plots for HBsAg actual values and change from baseline will be presented by study panel over time using color coding by category.

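### Time to virologic breakthrough and time to on-treatment flare count events during NA follow-up but censor event-free participants at EOT; if EOT means Week 24, the Kaplan-Meier curve after Week 24 cannot be interpreted.

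*SAP*

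**What the plan says.** **Event window.** For breakthrough, SAP 5.4.1.1.15 states: "On-treatment will be defined as the time period in which the participant receives any of the study interventions (including NA". For flares, SAP 5.4.1.1.16 states: "Off-treatment will be defined as the period after stopping all study interventions (including NA". A biochemical flare on NA alone is therefore an on-treatment flare. SAP 5.1.11 agrees: it ends the on-treatment period at the latest of three dates, one of them two days after the last NA dose. The breakthrough objective in SAP 1.1 covers the 24 weeks of treatment, "as well as during the FU period for participants who continue treatment with NA". SAP 1.2 has NA stopped at FU Week 2 if the completion criteria are met at Week 24; "otherwise NA treatment will continue during the complete FU period".

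**Censoring.** In SAP 5.4.1.3.6, participants who withdrew before a breakthrough "or who did not experience virologic breakthrough will be censored at the last available HBV DNA assessment at or before EOT". In SAP 5.4.1.3.7, participants without an on-treatment flare "will be censored at the last available blood markers or liver enzymes assessment at or before EOT". Neither section puts an upper limit on the event date.

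**Meaning of EOT.** The SAP's abbreviation list expands it only as end of treatment. SAP 5.5.1.5 gives it a time, in comparing the "HBsAg level at the last Follow-up timepoint and Week 24 (EOT"). The EOT2 label in SAP 5.1.3 is the last visit of treatment period 2.

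**Estimator.** SAP 5.4.2.3 specifies Kaplan-Meier for the cumulative incidence curve and for the median with a 90% CI. SAP 5.1.6 adds the quartiles.

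**The concern.** Kaplan-Meier needs participants with and without the event to be followed over the same window. Here, if EOT is Week 24, a participant on NA with no breakthrough leaves the risk set at Week 24, while one who breaks through at FU Week 12 stays in it until then. Whether someone is counted as at risk after Week 24 then depends on whether they later have the event. From the point where the last event-free participant is censored, the denominator consists only of future cases, and the curve must reach 100% at the last of them.

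The cap at EOT appears only on these two endpoints. Off-treatment flare and the other secondary time-to-event endpoints in SAP 5.4.1.3 censor at the last available assessment. Follow-up events are observable, because the protocol's Schedule of Activities continues HBV DNA and liver tests through FU Week 48. What is at stake is a plotted curve and median that could contradict the crude proportion printed beside them.

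**Working it through.** The documents give no expected rate, event count or precision target for these two endpoints, so there is no stated figure to reproduce. The calculation below is illustrative.

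**Inputs**
- N = 50, the planned enrolment (SAP 1.2).
- Week 24 is day 169 (24 × 7 + 1), FU Week 12 is day 253 (36 × 7 + 1), and FU Week 48 is day 505 (72 × 7 + 1).
- The Week 24 analysis window closes on day 183 (SAP 5.1.3).
- The event dates are chosen for illustration.
- k, the number still on NA and under observation at the follow-up event, is not in the documents and is an assumption.

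**Formula.** S(t) is the product over event times of (1 − d/r), with d events among r at risk. Cumulative incidence is 1 − S(t).

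**As written, with EOT read as Week 24**

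| Events | Event-free, censored day 169 | Steps | Kaplan-Meier incidence | Crude proportion |
|---|---|---|---|---|
| Day 253 | 49 | r = 1: S = 1 − 1/1 = 0 | 100%, median day 253 | 1/50 = 2% |
| Days 113 and 253 | 48 | r = 50: S = 0.98; r = 1: S = 0.98 × 0 = 0 | 2%, then 100% | 2/50 = 4% |
| Days 253 and 421 | 48 | r = 2: S = 0.5; r = 1: S = 0 | 50%, then 100% | 2/50 = 4% |

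Moving the first row's censoring date from day 169 to day 183 changes nothing.

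**Censoring matched to the event window.** Event-free participants continuing NA are censored at day 505 and those who stop NA at FU Week 2 (day 183). One event at day 253 gives 1 − (1 − 1/k) = 1/k:

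| Assumed k | 50 | 40 | 30 | 20 | 10 |
|---|---|---|---|---|---|
| Incidence | 2.0% | 2.5% | 3.3% | 5.0% | 10.0% |

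The median is not reached for any of these k.

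**Events restricted to Week 24 instead.** The same single-event data give 0%, with all 50 censored at Week 24.

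**Up to Week 24.** Everyone still under observation is in the risk set whatever happens to them later, so the estimate to that point is unaffected. The second row shows this: its first step is 1/50 = 2%.

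**The case against.** **EOT may mean the end of all treatment, including NA.** The abbreviation list allows this, and for the Week 24 milestone the SAP usually writes Week 24, EOSI, end of treatment period 2 or EOT2. Read together with SAP 5.1.11, EOT would fall at about Week 72 for participants who continue NA, and the censoring would be right. This objection stands in part: a reader might infer that the SAP fixes EOT at Week 24 for these endpoints, and it does not. The only timed use is in an exploratory HBsAg analysis. But it is the only timed use, and a programmer who follows it produces the faulty curve.

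**Only 24 weeks may have been intended.** SAP 5.4.1.2.1 calls the first 24 weeks on-treatment for its nadir intervals, and SAP 5.1 lists study intervention by treatment-period regimen. If events also stopped at Week 24 the estimate would be valid for that period. However, the event definitions and the breakthrough objective reach into follow-up, so in that case the event rule needs the correction.

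**The named endpoints are not affected.** This stands. SAP 1.1 lists the proportion with breakthrough and the frequency of flares. Those are analysed in SAP 5.4.2.1.14 and 5.4.2.1.15 without this censoring rule. Time to breakthrough and time to flare are not listed in SAP 1.1.

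**A late event may never happen.** The protocol (2.2.3.1) reports no breakthrough in any arm combining JNJ-6379 or placebo with NA in its Phase 2a study, and the documents give no expected rate here. The event and censoring counts reported with the curve would also show how little a 100% tail rests on. Both points lower the urgency; neither repairs the rule.

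**Conclusion.** The event window and the censoring date do not match as the text stands, and the SAP's only timing for EOT leads to the faulty version. On that reading, one event after the event-free participants have been censored takes the cumulative incidence to 100%, against 2% to 10% with matched censoring for assumed k from 50 down to 10.

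The damage is limited to the curve after Week 24 and any quartile, median or confidence limit that this part of the curve determines, and it arises only if a follow-up event occurs.

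A reader might infer that the whole Kaplan-Meier analysis is invalid, or that a listed objective is lost. The documents support neither: the curve to Week 24 is sound, and the listed proportions and frequencies stand. Nor is 2% for one event (or 4% for two) the settled correct answer, because it assumes that all 50 participants remain on NA and under observation.

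The study is exploratory, with no formal test. This should be fixed; it does not threaten the study's main conclusions.

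**What to change.** Define EOT in SAP 5.4.1.3.6 and 5.4.1.3.7, then align the two windows in one of two ways:

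1. Censor event-free participants at the last HBV DNA assessment (for flare, the last ALT/AST assessment) within the on-treatment period, including continuous NA in follow-up. This matches the event definitions and the breakthrough objective as written.
2. Count only events up to Week 24, keep the censoring at Week 24, and analyse follow-up on NA separately with Week 24 as the time origin.

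The cost is two sentences in the SAP and one derived censoring date in the time-to-event dataset. Study conduct and data collection do not change.

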5.4.1.3.7. Time to First Flare

Time to first biochemical flare (on- and off-treatment), clinical flare off-treatment, and virologic flare off-treatment will be evaluated.

Time to first on-treatment flare will be defined as the number of days between the date of first study intervention intake and the date of the first occurrence of on-treatment flare (i.e. the date of the first on-treatment flare [the first of the two confirmation visits] of each type- the date of first study intervention intake+1). The participants who withdrew early from the study before experiencing on-treatment flare or who did not experience on-treatment flare will be censored at the last available blood markers or liver enzymes assessment at or before EOT.

Time to the first off-treatment flare will be defined as the number of days between the date of last study intervention intake and the date of the first occurrence of off-treatment flare (i.e. the date of experiencing the first off-treatment flare [the first of the two confirmation visits] of each type- the date of last study intervention intake). The participants who withdrew early from the study before experiencing off-treatment flare or who did not experience off-treatment flare will be censored at the last available blood markers or liver enzymes assessment.

5.4.2. Analysis Methods

All secondary endpoints will be analyzed using the FAS. The analysis may be repeated in the IFN-FAS and modified FAS/IFN-FAS analysis sets if there is a difference of at least 2 participants between analysis sets.

Some analysis will be performed by group, as defined in Section 5.1.10. Summaries and graphs will be provided for each analysis phase, unless specified otherwise.

All secondary endpoints will be analyzed based on the observed case data. Additional analyses with specific imputation methods for missing data are added for selected endpoints.

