 - qq. *Visits at follow-up Week 16, 20, 28, 32, 40, and 44 are optional for participants who continue NA treatment and for participants who have restarted NA treatment during the follow-up period, provided that their HBV DNA and ALT values are stable.*
 - rr. Liver function tests only.
 - ss. Urine pregnancy tests will be provided to the participants for at home use as necessary to ensure urine pregnancy tests are performed at least every 4 weeks. Participants will report the results to the study site personnel at the next visit, and these will be added to the source documents. If positive, the participant should contact the site immediately.
 - tt. No JNJ-3989/PegIFN- α 2a will be administered or dispensed during follow-up. Administration/Dispensation of NA is only applicable for participants who could not stop NA treatment, or for those who met the NA re-treatment criteria. In between study visits, participants will take NA at home and they will bring their NA treatment with them to each study visit.
 - uu. If the NA treatment completion criteria are met at Week 24, treatment with NA will be stopped at FU Week 2.
 - vv. Available historical data on HBeAg status before start of NA treatment will be collected in the CRF.
 - ww. A urinalysis and urine chemistry sample will be taken at FU Week 2. In case of abnormalities, the tests should be repeated at the following visits.
 - xx. Includes close monitoring for neuropsychiatric adverse events during the PegIFN- α 2a treatment period. Participants who develop a neuropsychiatric adverse event during PegIFN- α 2a treatment, will be monitored closely until the neuropsychiatric adverse event resolves, with frequent (at least weekly) follow-up phone calls.
 - yy. NA treatment should be re-started in accordance with the NA re-treatment criteria (see Section 6.7.1, NA Re-treatment Criteria and Monitoring After Stopping of NA and Section 10.12 Appendix 12, for guidance after stopping NA treatment).
 - zz. Participants enrolled before Protocol Amendment 3 was in effect, may have received JNJ-6379 as part of their study intervention.

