- Any investigational agent, investigational vaccine, invasive investigational medical device, or investigational biological product (other than the study intervention taken in the context of this study).
Note: Approved COVID-19 vaccines or COVID-19 vaccines with conditional marketing authorization, emergency use authorization or special approval for emergency are allowed.

Disallowed from 6 months prior to baseline until end of follow-up:

- Any systemically (eg, intravenously, intramuscularly, orally, subcutaneously) administered medication that directly or indirectly interferes with immune responses (eg, cyclosporine, interleukins, systemic corticosteroids exceeding 5 mg of prednisolone equivalent/day).

Disallowed from screening until end of follow-up:

- Any anti-HBV drug (including vaccines) other than the study intervention taken in the context of this study.
Note: NA standard of care treatment is allowed between screening and baseline.
- Biotin (>1 mg daily dose), either taken alone or as part of a multivitamin formulation.
Note: The use of other vitamins is allowed.
- Topical steroids (>7 days) under occlusive dressing.

Note: The list of disallowed concomitant medication is not exhaustive; for products falling in one of the categories and not mentioned by name, the sponsor should be contacted to determine whether the product can be allowed.

The prescribing information for ETV, tenofovir disoproxil, TAF, and PegIFN- α 2a should be consulted for any additional prohibited medication. In case of flu-like symptoms after administration of PegIFN- α 2a, paracetamol up to a maximum of 2 g per 24 hours and a maximum of 6 g per week is allowed.

Medications requiring subcutaneous injection (other than JNJ-3989 and PegIFN- α 2a; eg, insulin) should be administered away from the JNJ-3989 and PegIFN- α 2a injection sites.

6.6. Study Intervention Completion at Week 24

With the implementation of Protocol Amendment 3, all participants had to stop JNJ-6379 treatment immediately.

Participants will stop treatment with JNJ-3989 and PegIFN- α 2a at Week 24 (EOSI). If all of the following NA treatment completion criteria are met at Week 24, treatment with NA will also be stopped at the next scheduled visit (ie, FU Week 2):

- The participant has ALT $<3x$ ULN, AND
- The participant has HBV DNA $<LLOQ$, AND
- The participant is HBeAg-negative, AND
- The participant has HBsAg <10 IU/mL.

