Note: In case of ALT elevation $\geq 3x$ ULN at Week 24, the investigator must consider different potential causes of increased ALT to ensure appropriate work up and management as needed. If the ALT elevation is unrelated to HBV activity and/or $<3x$ ULN by FU Week 2, NA completion may be considered at the discretion of the investigator and in consultation with the sponsor.

Participants who do not meet the above criteria at Week 24 should continue NA treatment during the 48-week FU Period.

If a participant prematurely discontinues investigational intervention before Week 24, follow-up assessments should be obtained as per the [Schedule of Activities](#) until 48 weeks after the end of investigational intervention unless the participant withdraws consent. In this case, NA treatment may be continued or, in consultation with the sponsor, discontinued, based on the above-mentioned NA treatment completion criteria.

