5.3.2.1.2. Observed Case Analysis

Only participants who have HBsAg data at Week 24 will be used for the analysis.

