5.4.2.1.2. NA Treatment Completion Criteria at Week 24 and During FU

The count and proportion of participants (and associated 90% CI) who met the NA treatment completion criteria at the end of treatment period 2, will be summarized.

Starting at end of treatment period 2, the incidence of participants who did not meet the NA treatment completion criteria will be summarized at each timepoint during the study, accompanied by the distribution of each of the 4 criteria that is not met. The NA treatment completion criteria are based on a threshold for the laboratory tests of ALT, HBV DNA, HBeAg and HBsAg.

The count and proportion of participants (and associated 90% confidence interval) who met the NA treatment completion criteria (Section 5.4.1.1.1) at any time during the FU phase will be summarized. All the NA treatment completion criteria will be checked based on clinical laboratory tests in FU phase.

5.4.2.1.2.1. NA Re-Treatment Criteria During FU

The count and proportion of participants (and associated 90% CI) who meet the criteria for NA re-treatment at any time during FU will be summarized descriptively. In addition, the count and proportion of participants (and associated 90% CI) who met the criteria according to the flag on the CRF page of 'NA Re-treatment Criteria Assessment' during the follow-up phase will be summarized over time.

The count and proportion of participants (and associated 90% CI) who re-started NA treatment during the follow-up phase on the basis of the ‘Study Drug Administration for NA’ CRF page will be summarized separately over time.

A cross-tabulation of participants who actually re-started NA treatment (re-started/not restarted) versus participants who met the above criteria (met/not met) will be presented over time.

5.4.2.1.2.2. HBsAg Cut-offs

The cut-offs for HBsAg values, decreases from baseline and RT will be used in separate summaries over time. The count and proportion of participants who meet those HBsAg thresholds during the study will be summarized descriptively by analysis phase over time and displayed in graphs like bar charts.

Cross-tabulations overtime of quantitative HBsAg (<LLOQ, ≥LLOQ) versus qualitative HBsAg (positive, negative), respectively, will also be presented.

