5.4.2.2. Continuous Endpoints

5.4.2.2.1. HBsAg, HBeAg, HBV DNA and ALT

Descriptive statistics on actual values [original unit and \log_{10} transformed values (except for ALT)], changes from baseline and changes from RT over time in HBsAg, HBeAg, HBV DNA and ALT will be summarized. Mean (+/- SE) plots of the values, change from baseline and change from RT over time will be presented by analysis phase. The change from baseline value to nadir (i.e. maximum decrease for each participant) in HBsAg, HBeAg and HBV DNA will be summarized descriptively. Box plots of the changes to nadir in HBsAg, HBeAg, and HBV DNA will display the distribution.

Change from baseline based on \log_{10} transform for quantitative HBsAg and HBeAg will be analyzed using mixed effects model for repeated measures [MMRM]) including analysis time point (week), baseline blood marker variable, and their interaction. The covariance structure will include a random intercept at the level of the participant to capture between-participant variability, while within-participant variability will be captured with an unstructured (type=UN) covariance matrix. In case of convergence problems, simpler variance-covariance structures such as Toeplitz or AR (1) will be considered. The selection of any of these structures will be determined after exploration of the observed correlation structure. The LS mean of change from baseline, standard error (SE), 90% confidence interval (CI) will be provided.

Descriptive statistics on actual values (original unit and \log_{10} transformed values) and changes from baseline (\log_{10} transformed values) at the end of treatment in HBsAg, HBeAg, HBV DNA and ALT (original unit) will be summarized by outcome response (i.e. by achieving a reduction of at least 2 \log_{10} IU/mL in HBsAg levels from baseline to Week 24, by NA treatment completion criteria status), by HBsAg seroclearance at the end of treatment period 2, FU Week 24 and FU Week 48, and by partial cure status at FU Week 24 and FU Week 48, and for participants who achieved functional cure at FU Week 24 and FU Week 48 if there is at least 10% response for each by-group.

Spaghetti plots for both absolute values and changes from baseline of HBsAg and HBV DNA will be presented over time per blood marker by selected subgroups (Section 5.7.5.1).

Waterfall plots for changes from baseline of HBsAg and HBeAg will be presented over time.

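### Six follow-up visits are optional on NA but required off NA, so all-participant observed-case summaries at those visits are not comparable with those at the visits everyone attends

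*SAP*

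**What the plan says.** **Schedule.** A footnote to the Schedule of Activities (Protocol 1.3) states: "Visits at follow-up Week 16, 20, 28, 32, 40, and 44 are optional for participants who continue NA treatment". It extends the option to participants who have restarted NA, and limits it for both groups: "provided that their HBV DNA and ALT values are stable". Participants off NA are seen every 4 weeks (Protocol 6.7.1), so the same six visits are required of them.

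**Who is off NA.** Under Protocol 6.6, NA is stopped only if four criteria are met at Week 24: "The participant has HBsAg <10 IU/mL", HBeAg-negative, HBV DNA <LLOQ and ALT <3x ULN (with some discretion on the ALT criterion). For everyone else: "Participants who do not meet the above criteria at Week 24 should continue NA treatment during the 48-week FU Period".

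**Analysis.** SAP Table 4 gives each of the six visits its own analysis window. On thresholds, SAP 5.4.2.1.2.2 says: "The cut-offs for HBsAg values, decreases from baseline and RT will be used in separate summaries over time". Sections 5.4.2.1.7 and 5.4.2.1.9 do likewise for HBeAg and HBV DNA. On means, Section 5.4.2.2.1 says: "Mean (+/- SE) plots of the values, change from baseline and change from RT over time will be presented by analysis phase". The missing-data rule is "All secondary endpoints will be analyzed based on the observed case data". The term is spelled out only for the primary endpoint (SAP 5.3.2.1.2): "Only participants who have HBsAg data at Week 24 will be used for the analysis". Read the same way at follow-up visits, a participant without data leaves the denominator.

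**What is not covered.** The LOCF rules (SAP 5.4.2.1.1) address only Follow-up Weeks 12, 24, 36 and 48. So do the missing-as-non-response analyses of functional and partial cure, and the extra summaries restricted to participants off NA (SAP 5.4.2.1.3.2, 5.4.2.1.10). The groups in SAP 5.1.10 split by JNJ-6379 exposure, and the subgroups in Table 8 use NA type at baseline. Neither uses NA status during follow-up.

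**The concern.** Absence at these six visits is built into the schedule, and it depends on NA status, which the Week 24 response determines. An observed-case table or curve over all follow-up visits therefore alternates between two populations: everyone still in follow-up at the required visits, and at the optional visits participants off NA plus whichever NA participants attend. A by-visit proportion can move between Follow-up Weeks 12 and 16, and move back at Week 24, with no participant's status having changed. In a bar chart or mean plot of durability, that movement would read as a fluctuating effect of treatment.

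**Working it through.** The documents give no figure for attendance or for the share stopping NA, so there is no plan figure on this point to reproduce. The exact 90% intervals in SAP Table 1 do reproduce (for example 25/50: 0.376-0.624), and the same method is used below. All rates that follow are assumptions.

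**Formula.** Let S be the number who stopped NA and all attend, C the number on NA, a the share of C attending, and s and c the proportions meeting a threshold in the two groups. Then

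observed proportion = (s x S + c x a x C) / (S + a x C).

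This takes attendance within C as unrelated to outcome, and it leaves out restarters. At a = 1 it equals the all-participant proportion, so there is no distortion.

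**HBsAg <10 IU/mL, simplest case** (N = 50, s = 100%, c = 0%):

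| Stoppers | a = 100% | a = 50% | a = 25% |
|---|---|---|---|
| 15 | 15/50 = 30% | 15/(15 + 17.5) = 46% | 15/(15 + 8.75) = 63% |
| 10 | 10/50 = 20% | 10/(10 + 20) = 33% | 10/(10 + 10) = 50% |

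**Less extreme rates, 10 stoppers and 40 continuers** (whole participants, rounded):

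| Threshold (s / c) | a = 100% | a = 50% | a = 25% | a = 0 |
|---|---|---|---|---|
| HBsAg <100 (80% / 30%) | 20/50 = 40% | 14/30 = 47% | 11/20 = 55% | 8/10 = 80% |
| HBsAg <10 (60% / 5%) | 8/50 = 16% | 7/30 = 23% | 6/20 = 30% | 6/10 = 60% |
| HBV DNA <LLOQ (40% / 95%) | 42/50 = 84% | 23/30 = 77% | 14/20 = 70% | 4/10 = 40% |
| HBV DNA <LLOQ (70% / 95%) | 45/50 = 90% | 26/30 = 87% | 17/20 = 85% | 7/10 = 70% |

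HBsAg proportions rise and HBV DNA suppression falls. Precision is lost as well: for HBsAg <100 the 90% interval goes from 0.28-0.53 (20/50) to 0.49-0.96 (8/10).

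**HBeAg.** These analyses use only HBeAg-positive participants (SAP 5.4.1.1.8), about 40% of 50 = 20. Those of them who stop NA by the criteria are HBeAg-negative at Week 24. If continuers skip a visit, the remaining denominator has been selected on the outcome itself.

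**Mean log HBsAg change.** Stopping depends on the level reached, not on the size of the fall, and entry requires only HBsAg >100 IU/mL (Protocol 5.1, A13.1). A fall from 150 to 9 is log10(150/9) = 1.2 log and meets the HBsAg criterion. A fall from 20,000 to 100 is log10(200) = 2.3 log and does not. The sign therefore depends on what is assumed, with 15 stoppers and 25% attendance:

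- Stoppers -2.8, continuers -1.6: the full-population mean is (15 x -2.8 + 35 x -1.6)/50 = -1.96, and the observed mean is (15 x -2.8 + 8.75 x -1.6)/23.75 = -2.36.
- The two values swapped: (15 x -1.6 + 35 x -2.8)/50 = -2.44, and (15 x -1.6 + 8.75 x -2.8)/23.75 = -2.04.

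**The case against.** A reader might infer that efficacy in general is inflated at these visits. The documents do not support that. The observed-case rule also covers HBV DNA and ALT. Participants entered suppressed on NA, and the stable ones are those who may skip, so their absence would tend to lower HBV DNA <LLOQ. For mean log HBsAg change the sign is open, as shown above.

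A reader might also infer that the denominator shrinks to the best responders. That is too strong as well. The visits are optional, not dropped. NA participants may attend, and those with unstable HBV DNA or ALT keep the visits as scheduled. Enriched for participants off NA is as far as the text goes.

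The plan has mitigations. The MMRM for HBsAg and HBeAg change draws on each participant's other visits and partly offsets the selection. Continuous summaries report the number of participants (SAP 5.1.6), and listings and spaghetti plots show every measurement. The study is exploratory with no formal test.

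These points limit the concern without removing it. The MMRM has no NA-status term and does not touch observed proportions, bar charts or raw mean plots. A printed n shows that participants are missing, but not that the loss was planned and tied to response.

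**Conclusion.** The point stands as a comparability problem at six follow-up visits. Following the SAP as written gives by-visit all-participant summaries whose denominator changes with NA status, and no planned analysis corrects this. Proportions below absolute HBsAg cut-offs and HBeAg clearance would tend to be too high there, and HBV DNA <LLOQ too low. The direction for mean log HBsAg change cannot be stated.

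The size is unknown until attendance and the share stopping NA are known. In the illustrations at 25% attendance, the HBsAg proportions shift by 14 to 33 points (16% to 30%; 30% to 63%); at full attendance the shift is zero.

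It would be wrong to conclude that the main durability results are compromised. The primary endpoint is at Week 24, the named Week 48 endpoints fall at Follow-up Week 24, and functional and partial cure are assessed at Follow-up Weeks 12, 24, 36 and 48. All of these visits are required of everyone. The change is worth making because it is cheap and prevents a misreading, not because a key result depends on it.

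**What to change.** In SAP 5.4.2, limit all-participant follow-up by-visit tables, bar charts and mean plots to the visits required of everyone: Follow-up Weeks 2, 4, 8, 12, 24, 36 and 48. Present Follow-up Weeks 16, 20, 28, 32, 40 and 44 by NA status (off NA; on or restarted NA), with the number attended over the number in follow-up in each group. Splitting by NA status is better than showing these visits only for participants off NA, because it keeps the data from NA participants who attend, including those with unstable HBV DNA or ALT for whom the visits are not optional.

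The cost is SAP wording, a visit filter and an NA-status flag at each visit. The downside is fewer time points on the all-participant curves.
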